Protocol

A Prospective, Randomized Clinical Trial of Two Periarticular Multimodal Drug Injections in Total Hip and Knee Arthroplasty

Principal Investigator

[name] MD

Version Date

June 9, 2016

Background

Perioperative pain control is a fundamental part of patient satisfaction. Many therapies are aimed at improving this critical component during a hospitalization. Current pain management techniques use several different mechanisms simultaneously and are termed "multi-modal". Multi-modal therapy has demonstrated improvement in pain control after surgery while minimizing side effects. Advancement in the understanding and practice of multimodal pain management is one of the prime reasons for shorter hospital stays.

A key component of the multimodal approach to pain management is the intra-operative surgical site injection of a local anesthetic or drug cocktail. There are many formulations used for this purpose. A formulation documented in the literature was implemented by this institution which has dropped the average length of stay dramatically. Concern over the limited half-life of the administered anesthetic and the continued need for opioid administration has led to a search for better drug formulations and administration vehicles. Recently, the FDA approval of an extended release bupivacaine called liposomal bupivacaine was thought to extend the effective half-life of the anesthetic agent and thereby prolong post-operative anesthesia. Use of liposomal bupivacaine in total joint surgery was almost universally adopted after its recent approval and has been an integral part of the "same day total joint" movement.

Upon the approval of liposomal bupivacaine by the FDA, there have been a number of studies examining the efficacy of the drug in the orthopedic patient population. Liposomal bupivacaine is expensive and adds to the burden of procedural cost. Studies, often conflicted by industry sponsorship, have suggested improvement in pain control and shortened hospitalizations with the use of liposomal bupivacaine. Other studies have raised questions about the effectiveness of this agent. Recently a randomized double blind study was performed with total knees which demonstrated no improvement in pain management with the addition of liposomal bupivacaine to the multimodal pain management protocol. This study has not been performed in the hip arthroplasty population.

Primary Objective:

The aim of this study is to determine whether the use of a liposomal bupivacaine based periarticular injection versus a ropivacaine based periarticular injection improves pain control in patients undergoing Total Hip and Knee arthroplasty at Kootenai Health. We intend to evaluate pain control by using a Pain Score measured every four hours during hospitalization.

Primary Outcome Variable

Pain Scores as averaged over length of stay. The Pain Scale routinely used at Kootenai Health will be utilized. This is the standard 0-10 scale with 0 being no pain to 10 which is the worst possible pain the patient has experienced.

Secondary Outcome Variable

Narcotic consumption (calculated in oral morphine equivalent dose)

Length of Stay (hours)

Setting/Resources for the Study

Kootenai Health will be the setting for the surgeries while [name] clinic will be the setting for subject recruitment. Subjects will be screened and enrolled by [name]. Surgery will be performed by [name]. Other surgeons may join the study but all will be performing the same injection technique. [name] will oversee the training of the surgeons and any other key research personnel that may join the study.

Study Design

This study will employ a prospective, randomized, double-blind, study design methodology.

Study Subjects

All subjects who have been routinely referred to [name] for total hip or knee arthroplasty will be screened for inclusion into this study.

Inclusion Criteria

- 30 - 85 years of age
- Hip or knee Arthritis (osteoarthritis, post traumatic, inflammatory, and avascular necrosis)

Exclusion Criteria

- Multiple daily doses of long acting Narcotics (such as Oxycontin, MS Contin, or Fentanyl patches etc.)
- Revision surgery
- Surgical complication (femoral fracture with implant insertion)
- Inability to provide Informed Consent

Subject Recruitment/Screening/Consent

Patients will be screened and consented during a routine pre-operative office visit to discuss their pending surgery. This will take place in a private consultation room to ensure privacy. It will be made very clear to patients that their participation is voluntary and that choosing not to participate in the study will in no way affect their future care by [name] or Kootenai Health.

Study Procedures

Total Hip and Knee arthroplasty is a standard procedure at Kootenai Health and routinely performed by the principal investigator. Patients will be randomized to either a ropivacaine based periarticular injection or a liposomal bupivacaine based periarticular injection (See Table 1).

Table 1. Periarticular Injection Assignments

Group A	Group B
20 mL Liposomal Bupivacaine	
25 mL Bupivacaine 0.5%	49.25 mL 5mg/ml Ropivacaine
1.0 mL 1:1000 Epinephrine	1.0 mL 1:1000 Epinephrine
0.8 mL Clonidine 100 mcg/mL	0.8 mL Clonidine 100 mcg/mL
13.7 mL NaCl 0.9%	13.7 mL NaCl 0.9%
1.0 mL Ketorolac (15 – 30 mg)*	1.0 mL Ketorolac (15 – 30 mg)*

*May be deleted for patients with compromised renal function

The randomization schedule will be set up using a routine alternating treatment assignment between each patient in a 1:1 pattern using an excel spreadsheet. The group assignment will be written on an order sheet and will be taken to the pharmacy where the pharmacist will mix the injection according to standard of care and as noted in Table 1. The Investigator will not be blinded to the treatment but the post-operative providers will be blinded to the randomized assignment group. An Advanced Registered Nurse Practitioner who routinely rounds on post-operative patients to evaluate their pain control will be blinded to the assignment group.

Early Withdrawal of Subjects

A patient may be withdrawn from the study prior to the expected completion of that subject for failure to adhere to protocol requirements, or subject consent withdrawal or the investigator may withdraw the patient for safety concerns. Patients may choose to withdraw from the study at any time. Data that have already been collected prior to consent withdrawal will still be used.

Statistical Plan

This is a non-inferiority trial. Therefore, the main output from the analysis above will be a 95% confidence interval for the difference between average pain scores for the hospitalization. It is anticipated that 118 130 patients will be enrolled into each cohort with an enrollment period of 3 years. A biostatistician will be consulting on the study and performing statistical calculations. Mean pain scores will be compared between the two groups within each cohort. Opioid use (morphine equivalents) will be compared from PACU admission to discharge. Length of stay, calculated in hours from the start of the surgical procedure until time of discharge, will be compared between the two groups within each cohort.

Potential Benefits

Patients may not benefit from their participation in this study and will receive usual care for patients undergoing Total Hip and Knee arthroplasty. It is hoped that their participation will enable the investigators to determine if there are differences in pain control between the two regimens for future patients.

Potential Risks

All procedures and medications used in this study are standard of care. The risks of bupivacaine and ropivacaine are noted in the tables below and the profiles are similar for drugs of this class. Patients may receive these medications outside the setting of this research.

Ropivacaine

Most common (>10%)	Common (5% - 10%)	Rare (<5%)
Nausea	Fever	Chills
Vomiting	Back Pain	Anxiety
Low Blood Pressure	Headache	Urine retention or low urine output
	Low blood count	High blood pressure
	Bleeding	Dizziness
	Low Heart Rate	Chest pain
	Itching	Low potassium
	Pain	Allergic Reaction: hives, rash, itching; sneezing, difficulty breathing; severe dizziness, vomiting, swelling of your face, lips, tongue or throat
	“Pins and Needles” feeling	Shortness of Breath
		Urinary tract infection, urgency, incontinence
		Numbness
		Heart Attack (<1%)
		Irregular heart rate
		Yellowing of the skin and eyes
		Low Magnesium level
		Blood clots in legs and/or lungs
		Coughing
		Agitation, confusion, sleepiness, nervousness, forgetfulness, inability to sleep, hallucination, nightmares
		Nervous Disorders: Trembling, coma, convulsions, weakness, eye drooping, stupor, pain or numbness in hands and feet
		Ringing in ears
		Muscle aches
		Fainting

Liposomal Bupivacaine

Most common (>10%)	Common (2% - 10%)	Rare (less than 2%)
Nausea	Fever	Chills
Vomiting	Dizziness	Rash
Constipation	Swelling in hands or feet	Urine Retention
	Low blood count	High blood pressure
	Bleeding	Lightheadedness

	Low blood pressure	Neck pain
	Itching	Numbness and tingling in the mouth or lips
	Fast heart rate	Allergic Reaction: hives, red rash, itching; sneezing, difficulty breathing; severe dizziness, vomiting, swelling of your face, lips, tongue or throat
	Headache	Shakiness
	Inability to sleep	Low heart rate
	Muscle spasms	Irregular heart rate
	Back pain	Ringing in the ears
	Sleepiness	Blurry vision
		Low oxygen level
		Pain
		Anxiety, confusion, depression, agitation, restlessness,
		Swelling at the incision site

The formulation of liposomal bupivacaine allows for a longer duration of action and a slower absorption into systemic circulation, avoiding high plasma concentrations. Local infiltration can result in significant system plasma concentrations for up to 96 hours; however, significant levels are not correlated with local efficacy and differ between surgical procedures. Because of the longer lasting plasma concentrations there is concern for potential drug interactions should another local anesthetic be used during this 96-hour time period. Kootenai Health recently instituted a procedure placing a colored armband on every patient receiving liposomal bupivacaine and providing written information about the drug including time the drug was given and when the 96-hour time period is over. Patients are blinded to their treatment assignment and to maintain the blind, all study patients will receive the armband and information. This will provide the same standard of care to participants randomized to the liposomal bupivacaine group and will not incur risk to those randomized to the ropivacaine group. This information will be included in the consent form.

Breach of confidentiality is a risk of this study in the transfer of data for research purposes.

Reporting of Serious Adverse Events

Reports of unanticipated adverse events will be submitted to the IRB upon discovery following the correct policies and procedures. Copies of each report and documentation of IRB notification and receipt will be kept in the Investigator's records.

Data and Safety Monitoring Plan

Because both groups are receiving well established standard of care treatment, the Principal Investigator will oversee the safety of the study. This safety monitoring plan will include careful assessment and appropriate reporting of adverse events as noted above. Ongoing evaluation of subject eligibility, adverse events, and the informed consent process will occur with compliant reporting to the IRB of protocol deviations. The Principal Investigator will closely monitor for

trends in the data or a higher than expected rate of occurrence for any adverse effect such as a higher than expected use of pain medication in either group.

In addition, a blind interim analysis of the data will be conducted by the statistician when 50% of the sample is accrued. If the results show statistically overwhelming significant differences between groups, the blind will be broken and the study stopped.

Confidentiality and Management and protection of Data

Information about study subjects will be kept confidential and managed according to the Health Insurance Portability and Accountability Act of 1996 (HIPAA).

Patient data will be entered into electronic spreadsheets and paper data forms. One spreadsheet, enrollment form, will contain the patient name, medical record number, study number and randomization group. The second spreadsheet will contain the study number, patient demographic and study data. Only the investigators will have access to the files and their passwords. Data will be stored on the Kootenai Health protected and secured main computer system. Any paper records will be stored in hard copy in a locked filing cabinet in the investigator's office for a minimum of five years. At this time the information will be destroyed in accordance with the Kootenai Health document destruction policy. An electronic database such as REDCap may be used for data storage and will have password protected, limited access.

Results and Publication Plan

The data from this study will be shared at Kootenai Health. External dissemination of the results in journal publication is under consideration. All data will be aggregated and de-identified.

Medical Care and Compensation for Injury

If patients are injured from taking part in this research study, medical care will be provided. The costs of the care will be billed to the patient or his/her insurance. No funds have been set aside to pay the patient in the event of a research related injury. Study participants will be instructed to contact the investigator for more information.

References

3. Schroer, W. A prospective randomized periarticular trial of liposomal bupivacaine. Paper #2. Presented at: American Association of Hip and Knee Surgeons Annual Meeting; Nov. 7-9, 2014; Dallas.

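### The trial is called randomised, but its only stated allocation method is patient-by-patient alternation with no concealment, so each assignment can be predicted from the one before it on the same list

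*Combined protocol and SAP*

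**What the plan says.** The word randomised appears in three places. The title reads "A Prospective, Randomized Clinical Trial of Two Periarticular Multimodal Drug Injections in Total Hip and Knee Arthroplasty". Study Design says "This study will employ a prospective, randomized, double-blind, study design methodology". Study Procedures says "Patients will be randomized to either a ropivacaine based periarticular injection or a liposomal bupivacaine based periarticular injection".

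The method comes after Table 1 in Study Procedures: "The randomization schedule will be set up using a routine alternating treatment assignment between each patient in a 1:1 pattern using an excel spreadsheet". Nothing else in the protocol describes how the sequence is generated. No random-number source, blocks, strata or minimisation are mentioned.

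On implementation, the same section says "The group assignment will be written on an order sheet and will be taken to the pharmacy", so the group is already fixed when the pharmacy receives the sheet. It adds: "The Investigator will not be blinded to the treatment but the post-operative providers will be blinded to the randomized assignment group". The section on confidentiality and data management says "One spreadsheet, enrollment form, will contain the patient name, medical record number, study number and randomization group" and "Only the investigators will have access to the files and their passwords".

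The protocol does not say when a group is assigned relative to consent, who assigns it, or whether hips and knees share one list.

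**The concern.** Random allocation makes the assigned arm unrelated to prognosis. Alternation does so only if nobody who can influence who enters, or in what order, acts on the known next arm. Here the next arm is open to anyone who knows the previous one, and the protocol describes nothing to prevent that knowledge.

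The main output in the Statistical Plan is a 95% confidence interval for the difference in average pain score. Its stated coverage assumes that assignment is independent of prognosis. If patients expected to have more or less pain were invited, deferred or ordered according to the coming arm, the interval would be centred on the wrong value. Blinding of patients and post-operative staff could not correct this, because it acts after assignment. The plan names no adjustment for baseline factors either.

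**Working it through.** **1. Label against method.** Three statements say randomised, and one statement gives the method, which is a fixed rule. No other text replaces or qualifies it. The removal of names does not explain this, because a removed name cannot hide a method.

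**2. Who could know the next arm.** The investigator is unblinded, and the investigators can open the enrolment file. That file shows past assignments; nothing says it also holds future ones. Under alternation, past assignments are enough. The enroller's name is removed, so it is an inference that the enroller has this knowledge.

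**3. Predictability.** This is the expected share of correct guesses by someone who knows all earlier assignments on the list. The Statistical Plan prints both 118 and 130 per cohort, so both are used.

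- Alternation, with the first patient a coin toss: (0.5 + n − 1)/n. For n = 118, 117.5/118 = 99.6%. For n = 130, 129.5/130 = 99.6%. Every assignment after the first is known.
- Simple randomisation: 50%.
- Permuted blocks of one known size 2m: [m + (2^(2m)/C(2m,m) − 1)/2]/(2m).
  - Size 4: [2 + (16/6 − 1)/2]/4 = 70.8%.
  - Size 6: [3 + (64/20 − 1)/2]/6 = 68.3%.
  - Size 8: [4 + (256/70 − 1)/2]/8 = 66.6%.
- Permuted blocks of randomly varying size, by simulation (block sizes are assumptions):

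| Block sizes | Guess the arm with fewer patients so far | Guess the opposite of the last assignment |
|---|---|---|
| 4, 6 | 69% | 60% |
| 4, 6, 8 | 68% | 58% |
| 6, 8, 10 | 66% | 56% |

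If hips and knees have separate alternating lists, someone tracking the last assignment within the joint still predicts every later one. Someone who knows only the last assignment overall is right about 75% of the time (simulation, 260 patients, equal random mix of joints). The matching figure for joint-stratified blocks of 4, 6 and 8 is about 54%.

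**4. Effect on the result, as illustration.** The documents give no SD, margin or selection shift, so all three are open. Let δ be a difference in mean pain between arms produced by selection alone. The noncentrality is δ/(SD·√(2/n)), with n per arm and 2n − 2 degrees of freedom. For n = 65, SD 2 and δ = 0.1, this is 0.1/(2 × √(2/65)) = 0.285, against a critical value of 1.979. The one-sided error is evaluated at the margin, so it does not depend on the margin's value.

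| Shift (points) | One-sided 2.5% error becomes | Two-sided 5% error becomes |
|---|---|---|
| 0 | 2.5% | 5.0% |
| 0.1 favouring the tested arm | 4.7% (4.1 to 5.7%) | 5.9% (5.5 to 6.7%) |
| 0.3 favouring the tested arm | 13.3% (9.5 to 20.4%) | 13.6% (9.9 to 20.5%) |

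The main figures use 65 per arm and SD 2. The ranges cover SD 1.5 to 2.5 and 59 to 65 per arm, which is 118 or 130 per cohort split 1:1. Reading the sample-size sentence as 130 per arm raises the upper ends to 7.7% and 8.3% for 0.1 point, and to 36% for 0.3 point. In the opposite direction the one-sided error falls, to 1.2% at 0.1 point and 0.25% at 0.3 point (65 per arm, SD 2).

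**The case against.** The best defence is that no bias has been shown. Study Subjects says all referred patients are screened, patients and post-operative providers are blinded, and the safety monitoring section provides for eligibility review and reporting of deviations to the IRB. Alternation also delivers the intended 1:1 split exactly.

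It is true that no bias is shown. The safeguards, however, address other problems. Screening everyone limits selective approach but not deferral or ordering. Blinding acts after assignment. Changing the order of eligible patients need not break any stated rule, so deviation reporting would not reveal it. Equal numbers are not equal prognosis.

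Three narrower points stand:

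- Certainty of prediction requires knowing the last assignment on the same list. With separate hip and knee lists and knowledge only of the last patient overall, it drops to about 75%.
- The protocol compares two groups within each cohort, so 59 to 65 per arm is the better reading, and the 36% figure should not be treated as typical.
- Nothing in the documents links predictability to a shift of 0.1 or 0.3 points. Any bias of that size would give the same error rates, so the second table shows sensitivity and does not estimate what alternation did.

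None of these removes the contradiction between label and method.

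**Conclusion.** The concern holds and must be fixed. The allocation described is deterministic and unconcealed, so the design as written is quasi-randomised. This follows from the text and needs no assumption. The certainty of prediction also follows, given knowledge of the last assignment on the same list.

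That selection took place is not established, and whether the enroller holds the needed knowledge is inferred. The error rates rest on an assumed SD, arm size and shift; with no selection the error stays at its nominal level. On the better reading of arm size, a 0.3-point shift could take the one-sided error to about 20% at most over the SD range used.

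**What to change.** Replace the alternation sentence in Study Procedures with:

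> Assignments come from a computer-generated random list prepared by the consulting biostatistician, in permuted blocks of randomly varying size, stratified by joint (hip or knee). Block sizes are not disclosed to enrolling staff. The list is held by the pharmacy, and each assignment is released only after consent and eligibility are recorded.

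Change the order sheet so that it requests a study injection and the pharmacy assigns the group. Keep upcoming assignments out of any file that enrolling staff can open. Another holder independent of enrolment, such as the biostatistician, would also serve.

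If some patients have already been assigned by alternation, describe that part as quasi-randomised, show baseline balance by arm, and add a sensitivity analysis that excludes it. If enrolment finished under alternation, nothing remains to analyse after exclusion, so the relabelling and the baseline comparison are what is left.

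**Cost.** A protocol amendment, one list from a biostatistician already consulting, and an added step for a pharmacy already mixing the injections. No extra patients or procedures are needed if no one is enrolled; otherwise the randomised part is smaller than planned.

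**Limits.** The investigator remains unblinded, so someone tracking every past assignment could still guess the next about 66% to 69% of the time, depending on block sizes. Withdrawal of patients by someone who knows the arm is not addressed. Simple randomisation would cut guessing to 50% but would not hold the arms level: the 95% range for one arm is 54 to 76 of 130. In the simulated block lists the largest difference between arms was 2 to 4 patients, so varying blocks are a reasonable compromise.

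### Assignment is not stated to be separate for hips and knees, although pain and length of stay are compared within each cohort (minor)

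*Combined protocol and SAP*

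**What the plan says.** In the combined protocol and SAP, Study Procedures sets the assignment rule as "a routine alternating treatment assignment between each patient in a 1:1 pattern using an excel spreadsheet". The unit is the patient; the sentence mentions no joint, stratum or second schedule. The section on confidentiality and data protection adds that "One spreadsheet, enrollment form, will contain the patient name, medical record number, study number and randomization group", and lists no field for joint.

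The Statistical Plan works at a different level: "Mean pain scores will be compared between the two groups within each cohort". Length of stay also "will be compared between the two groups within each cohort". The sentence between these two gives no cohort: "Opioid use (morphine equivalents) will be compared from PACU admission to discharge". Enrolment is planned per cohort, with 118 and 130 printed side by side.

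Cohort is not defined. The trial enrols hip and knee arthroplasty patients and each cohort contains two treatment groups, so joint is the natural reading. The documents do not say whether hips and knees share one schedule, or whether assignment follows the order of consent, enrolment or surgery.

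**The concern.** A comparison made within each joint is most precise when the arms are equal within each joint. The written rule secures equal numbers only over consecutive patients. Alternation also has a period of two. If one sequence covers both joints and the joints tend to arrive in alternating order, the two patterns line up and one joint drifts into one arm without anyone intending it. At stake is the width of the confidence interval in each cohort. For any outcome pooled over joints, the arm contrast could also absorb a difference between hip and knee patients.

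**Working it through.** **Inputs from the documents.** Ratio 1:1 by patient-level alternation (Study Procedures); m = 118 or 130 per cohort (Statistical Plan, both carried); 95% confidence interval (Statistical Plan). The plan gives no margin, standard deviation or power, so its enrolment figure cannot be reproduced. Results are therefore relative to an even split, or in SD units.

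**Assumptions.** Cohort means joint; the stated number is the cohort total; one sequence covers 2m patients; equal numbers of hips and knees are expected.

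**Formulas.** With nA and nB patients in the arms of a cohort of n:
- information relative to 1:1 = 4 × nA × nB / n²
- 95% half-width in SD units = 1.96 × √(1/nA + 1/nB)

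**1. Balanced reference.** 59:59 gives 1.96 × √(2/59) = 0.361 SD. 65:65 gives 1.96 × √(2/65) = 0.344 SD.

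**2. One alternating sequence, joints in random order.** The number on one arm within a cohort is Hypergeometric(2m, m, m).

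| m | SD of arm count | 95% range of split | Information at limit | Half-width at limit |
|---|---|---|---|---|
| 118 | 3.85 | 51:67 to 67:51 | 4×51×67/118² = 0.982 | 0.364 SD |
| 130 | 4.04 | 57:73 to 73:57 | 4×57×73/130² = 0.985 | 0.346 SD |

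Mean loss = 4 × variance / m²: 4 × 3.85² / 118² = 0.4%, and 4 × 4.04² / 130² = 0.4%. A split of 60:40 or worse has probability 0.3% (m = 118) or 0.2% (m = 130). If the cohort sizes may also vary, simulation gives about 2% loss at the 2.5th percentile.

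**3. One alternating sequence, joint order tending to alternate.** Let s be the assumed chance that the next assigned patient has the other joint. Simulation of 260 patients (m = 130):

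| s | Mean information | Mean loss | 2.5th percentile of information | Loss there |
|---|---|---|---|---|
| 0.5 | 0.996 | 0.4% | 0.980 | 2% |
| 0.7 | 0.991 | 0.9% | 0.955 | 4.5% |
| 0.8 | 0.984 | 1.6% | 0.922 | 8% |
| 0.9 | 0.967 | 3% | 0.838 | 16% |

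Interval width scales as 1/√information. An 8% loss widens it by 1/√0.922 = 1.04, and a 16% loss by 1/√0.838 = 1.09. With m = 118 the losses are slightly larger.

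**4. Fixed orders.** Strict H-K-H-K with nobody skipped gives 130:0 in one joint and 0:130 in the other (118:0 and 0:118). H-H-K-K, or all hips then all knees, gives exact balance (65:65 or 59:59).

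**5. How much alternation is plausible.** Suppose the underlying order alternated perfectly and each patient entered independently with probability q. The next entrant has the other joint after an odd number of steps, so s = q / (1 − (1 − q)²) = 1 / (2 − q). Then q = 0.7 gives s = 1/1.3 = 0.77; s = 0.8 needs q = 0.75; s = 0.9 needs q = 0.89.

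**6. Opioid use, if pooled over joints.** The distortion of the arm contrast is (difference between arms in hip share) × (hip-minus-knee difference in mean opioid use). At 57:73 the hip shares are 73/130 = 56% and 57/130 = 44%, a gap of 12 percentage points. In simulation with m = 130, the gap reaches 14 points or more in 2.5% of trials at s = 0.5, and 41 points or more at s = 0.9. The documents give no hip-knee difference in opioid use, so the distortion cannot be expressed in morphine equivalents.

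**7. After the fix.** Alternation kept separately within each joint holds each cohort within one patient of 1:1. Random blocks within joint hold it within half a block.

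**The case against.** The strongest reply is that the shared sequence is inferred and that the loss is small on any likely order. Both parts largely stand. The assignment sentence does not say that hips and knees share a list, and the single enrollment spreadsheet is a statement about data storage. No operating list is mentioned. Consent takes place at a pre-operative office visit, so assignment could follow consent order. Participation is voluntary and there are exclusions, so skipped patients would break up any regular order; step 5 shows that s = 0.9 needs near-complete enrolment on top of perfect alternation.

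A reader might go further and infer four things that the documents do not support:
- **That one arm of each cohort will be empty.** This needs strict H-K-H-K throughout with nobody skipped; other regular orders balance exactly.
- **That a single random list would be no better.** It would remove the systematic alignment of joint and arm. What remains is chance imbalance, costing under 1% of information on average.
- **That the pain comparison is biased.** Unequal numbers alone do not bias a difference in means within a cohort.
- **That opioid use will be pooled.** The sentence stands between two that specify within-cohort comparisons, so omission of the phrase may be accidental.

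What survives is the omission: nothing written secures balance within the unit of analysis, and the opioid comparison has no stated unit.

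**Conclusion.** The point holds as a minor gap between allocation and analysis. The protocol does not state whether assignment is separate by joint, while two of its three outcomes are compared within cohort. If one sequence serves both joints and their order is haphazard, the cost is negligible. It becomes material only if joint order tends to alternate, and the switching probabilities behind the larger losses are assumptions, not figures from the documents. The effect is on precision; confounding arises only for an outcome pooled across joints.

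The conclusion rests on reading cohort as joint and on a shared sequence. If separate lists are already intended, one sentence saying so closes the point.

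The graver weakness in the same assignment sentence is that alternation is predictable and the investigator is not blinded to treatment. That is a separate matter, but it limits which remedy is worth adopting here.

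**What to change.** In Study Procedures, state that hips and knees each have their own assignment sequence, preferably concealed, computer-generated random blocks stratified by joint. Two separate alternating lists would restore balance within each joint, but the next assignment would still be predictable to the unblinded investigator. In the Statistical Plan, define cohort as joint, if that is what is meant, and state that opioid use is also compared within cohort.

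The cost is a second list and a few sentences of text. No extra patients, staff or procedures are needed.
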